4.2 Discussion for Study Design, Including the Choice of Control Groups

This is an open-label, non-randomized study; all subjects enrolled in this study will be treated with HGT-1410. Subjects will initially receive the same dose of HGT-1410 they received in Study HGT-SAN-055.

4.3 Method of Assigning Subjects to Treatment Groups

All subjects enrolled in this extension study initially received doses of HGT-1410 Q4W via an IDDD at the same dose (10, 45, and 90 mg) as the group to which they were assigned in Study HGT-SAN-055:

- Group 1: HGT-1410 administered by IT injection 10 mg once per month (Q4W)
- Group 2: HGT-1410 administered by IT injection 45 mg once per month (Q4W)
- Group 3: HGT-1410 administered by IT injection 90 mg once per month (Q4W)

Subjects assigned to Group 1 had their dose increased to 45 mg Q4W at the first administration of HGT-1410 following full approval of Protocol Amendment 4.

4.4 Blinding

There was no blinding to study drug as this is an open-label study.

4.5 Randomization

There was no randomization to treatment in this study.

4.6 Determination of Sample Size

Since this was an extension study, sample size was determined by the number of subjects who completed HGT-SAN-055 (maximum of 12 subjects) and elected to continue treatment with HGT-1410 in this study. Hence no statistical estimation of the sample size was performed.

5 EFFICACY AND SAFETY VARIABLES

5.1 Schedule of Evaluations

The schedule of evaluations can be found in Section 9.4 of this SAP, which can also be found in Appendices 1 of the study protocol (Amendment 7).

5.2 Primary Endpoints

The primary endpoints of this study were related to the long-term safety of intrathecal HGT-1410 administration. The safety endpoints were:

[figure not shown]
- AEs (type and severity)
- changes in clinical laboratory testing (serum chemistry including liver function tests, hematology, and urinalysis)
- electrocardiograms (ECG)
- CSF chemistries (including cell counts and inflammatory markers)
- anti-rhHNS antibodies (in CSF and serum).

5.3 Secondary Endpoints

The secondary endpoints of this study were to collect over an extended treatment period (as the change from baseline [defined as the start of the HGT-SAN-055 study]) clinical and potential surrogate biomarker efficacy data:

- Measures of standardized neurocognitive and behavioral assessments, Sanfilippo-specific behavioral rating scales, gross and fine motor assessments, functional adaptive rating scales, QoL questionnaires, and Children's Sleep Habits Rating Scale.
- Concentration of safety and potential surrogate efficacy biomarkers in CSF, urine, and serum.
- Concentration of heparan sulfate (HS) and HS derivatives in CSF and glycosaminoglycan (GAG), including HS and HS derivatives, in urine.
- Brain magnetic resonance imaging (MRI) and auditory brainstem response (ABR), (also known as Brainstem Auditory Evoked Potentials).

5.4 SOPH-A-PORT Mini S Assessments

6 STATISTICAL ANALYSIS

6.1 General Methodology

All statistical analyses will be performed using SAS[®] Version 9.3 or later.

Tabular summaries will be presented by rhHNS dose group (10, 45, and 90 mg). Continuous variables will be summarized using descriptive statistics [sample size (N), mean, standard deviation (SD), minimum, median, and maximum]. Categorical variables will be summarized using the number and percentage in each category. Graphical techniques will also be used to assess trends across time per treatment group. In particular, spaghetti plots to help visualize the trajectories or time trends of individual subjects within the same plot will be used. For all analyses, baseline will be the measurement from the day the subject received their first IT dose of HGT-1410 in Study HGT SAN 055. Results (e.g., mean, SD) from all visits will be displayed with significant digits consistent with the measured precision of the test or original value.

For samples associated with multiple tests performed at the same visit (e.g. lab results), the latest valid result will be selected for analysis.

6.2 Analysis Populations

The safety population is the only analysis population in this study. The safety population will consist of all eligible subjects from HGT-SAN-055 who have agreed to participate in the extension study, HGT-SAN-067. This population will be used to perform both safety and efficacy analyses.

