2 INTRODUCTION

2.1 Background

This study, HGT-SAN-067, is an open-label, long term, multicenter, extension of Study HGT-SAN-055. The study is designed to evaluate the long-term safety, clinical activity, and biomarker outcomes of intrathecal (IT) administration of 3 dose levels (10 , 45 , and 90 mg once per month [Q4W]) of recombinant human heparan N-sulfatase (rhHNS, HGT-1410) via an intrathecal drug delivery device (IDDD) in subjects with Sanfilippo Syndrome Type A (MPS IIIA) who successfully complete the Phase I/II study HGT-SAN-055 (including end of study [EOS] assessments) and elect to continue to receive HGT-1410 treatment.

This statistical analysis plan (SAP) provides a technical and detailed elaboration of the planned statistical analyses for protocol HGT-SAN-067. Populations for analyses, data handling rules, statistical methods, and formats for data presentation are provided. The statistical analyses and summary tabulations described in this SAP will provide the basis for the results sections of the clinical study report (CSR).

The structure and content of this SAP provides sufficient detail to meet the requirements identified by the Food and Drug Administration (FDA) and International Conference on Harmonization (ICH) of Technical Requirements for Registration of Pharmaceuticals for Human Use.

This SAP is based on protocol HGT-SAN-067 Amendment 7, dated 08 February 2016. The reader of this SAP is encouraged to also read the clinical protocol for details on the conduct of this study and the operational aspects of clinical assessments and timing for completing a subject in this study

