4 STUDY DESIGN

4.1 General Description

Study HGT-SAN-055 was a multicenter, multiple-dose, dose escalation study designed to evaluate the safety, tolerability, and clinical activity of up to 3 dose levels ([10, 45, and 90 mg] monthly for 6 months) of rhHNS administered via an IDDD in subjects with MPS IIIA. The study was planned to enroll up to 15 subjects to ensure a total of 12 subjects who completed the study (4 subjects per dose group). The primary objective was to determine the safety and tolerability of rhHNS via ascending doses administered via a surgically implanted IDDD once monthly for 6 months, in subjects with MPS IIIA. Safety was assessed through adverse events (AEs; types and severity), changes in clinical laboratory tests (serum chemistry, hematology and urinalysis), electrocardiograms (ECGs), cerebrospinal fluid (CSF) chemistries (including cell counts and inflammatory markers), and anti-rhHNS antibodies (CSF and serum). Secondary endpoints include the determination of the concentration of rhHNS in CSF and serum, and changes in CSF biomarkers. Additional secondary endpoints of potential efficacy included neurocognitive and developmental testing, quality of life measurements, and neurological assessments.

Long-term safety, clinical activity and biomarker outcomes of IT administration of rhHNS have been evaluated through the extension study, HGT-SAN-067. Subjects continued in the same treatment group they were assigned to in the HGT-SAN-055 study, with the exception of subjects in the 10 mg group who started transitioning in July 2013 to the 45 mg group following Protocol Amendment 4 (dated 03 May 2013). For all analyses under this SAP, subjects will be presented under the original treatment arm assigned in HGT-SAN-055. Analyses will be conducted on combined data from HGT-SAN-055 and HGT-SAN-067. In order to maintain a nomenclature system based on study chronology across the original HGT SAN-055 study and this extension study, the Baseline Visit for this extension study will be considered to be the day the subject received their first IT dose of HGT-1410 in Study HGT SAN 055.

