7.9.1 Adverse Events

Aes will be recorded throughout the study and at early termination. Aes will be coded using the Medical Dictionary for Regulatory Activities (MedDRA) version 13.1 or higher.

Treatment-emergent Aes, defined as all Aes from the time of the surgery for first IDDD implantation in HGT-SAN-055 to the last day of reporting period (or cut-off date), will be summarized by treatment group. The summary will include the number and percentage of subjects with any AE, any drug-related AE, any surgery-related AE, any IDDD-related AE, any IT administration process-related AE, any severe AE, any serious AE (SAE), any serious drug related AE, and any AE that lead to discontinuation.

Treatment emergent Aes will be summarized by system organ class (SOC) and preferred term by dose group. The number and percentage of subjects experiencing an AE will be tabulated; recurrent Aes observed within a subject will be counted once. Furthermore, treatment-emergent Aes deemed as possibly/probably or definitely related to device surgical procedure, IDDD, investigational product, and IT administration process will be summarized separately. Treatment-emergent SAEs and treatment-emergent Aes which lead to study discontinuation will be similarly summarized.

By-subject listings will be provided for treatment-emergent Aes, treatment-emergent SAEs, deaths, and treatment-emergent Aes leading to discontinuation.

In general, an AE will be considered a treatment emergent AE if it cannot be definitively categorized by the available components (day, month, year) of the AE onset date with respect to the date of the IDDD implantation.

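### Adverse events are counted from first implantation in HGT-SAN-055, but only in subjects who completed that study and continued, so deaths and adverse-event withdrawals in HGT-SAN-055 are zero by construction

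*SAP*

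**What the plan says.** Section 6.2 is explicit that there is one population for both safety and efficacy: "The safety population is the only analysis population in this study". It is defined by the decision to go on: "The safety population will consist of all eligible subjects from HGT-SAN-055 who have agreed to participate in the extension study, HGT-SAN-067". Section 2.1 gives the entry condition for the extension, describing subjects "who successfully complete the Phase I/II study HGT-SAN-055 (including end of study [EOS] assessments) and elect to continue to receive HGT-1410 treatment". Section 4.6 repeats it, sizing the study by the HGT-SAN-055 completers, at most 12, who elected to continue.

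The event window starts earlier. Section 7.9.1 describes treatment-emergent adverse events as "defined as all Aes from the time of the surgery for first IDDD implantation in HGT-SAN-055 to the last day of reporting period". Section 4.1 pools the data: "Analyses will be conducted on combined data from HGT-SAN-055 and HGT-SAN-067". The same section shows that non-completion of HGT-SAN-055 was foreseen, since that study was "planned to enroll up to 15 subjects to ensure a total of 12 subjects who completed the study".

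The adverse event tables in Appendix II and the listings of deaths and of events leading to discontinuation in Appendix IV are all titled for this safety population. So is the disposition table, although it is laid out by study. None of the adverse event tables is split by study period. The addendum (its Section 5.2) adds a device follow-up population, but it is drawn from HGT-SAN-067 subjects and brings back nobody who left earlier.

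**The concern.** The clock starts at first surgery, while membership of the population is settled about 6 months later, after the monthly doses of HGT-SAN-055. A subject who died in that interval, or who stopped because of the drug, the surgery or the device, is absent from both numerator and denominator. Those who got through it contribute the same interval as time at risk. Completers who declined to go on are absent as well, and their choice may have depended on tolerability.

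Long-term safety is the primary objective and adverse events are a primary endpoint, so this affects the main output even of an abbreviated report. The interval concerned also contains the first implantation and early use of the device, and Section 4.1 itself reports more complications than expected with the first device. As titled, no listed output would show a reader that anyone had been left out.

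**Working it through.** **Inputs.** Planned enrolment in HGT-SAN-055: up to 15 (Section 4.1). Planned completers: 12, as 4 in each of 3 dose groups (Section 4.1). Maximum for HGT-SAN-067: 12 (Section 4.6). The SAP does not give the number who actually stopped HGT-SAN-055, their reasons, or how many completers declined to continue.

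**1. The plan's own figure.** 3 groups × 4 completers = 12, which agrees with the maximum in Section 4.6. The enrolment allowance leaves 15 − 12 = 3 possible non-completers, and 3/15 = 20%.

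**2. The structural zero.** Membership requires eligibility, and eligibility requires completing HGT-SAN-055. Consent could be given from Week 20 of that study, but early consent does not remove the completion requirement. So no member can have died in HGT-SAN-055 or withdrawn from it. The zero concerns withdrawals that took place in HGT-SAN-055. An event that began there and led to withdrawal later, in HGT-SAN-067, would still be counted.

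**3. Size for adverse events leading to withdrawal from HGT-SAN-055.** Assume that all 12 completers continue and that k further subjects stopped because of an adverse event. The planned population shows 0/12 whatever k is. Counting everyone implanted or dosed gives k/(12 + k):

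| k (assumed) | Planned population | All implanted or dosed |
|---|---|---|
| 0 | 0/12 (0%) | 0/12 (0%) |
| 1 | 0/12 (0%) | 1/13 (7.7%) |
| 2 | 0/12 (0%) | 2/14 (14.3%) |
| 3 | 0/12 (0%) | 3/15 (20.0%) |

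Exact (Clopper-Pearson) 95% intervals, which the plan does not call for, are 0 to 26.5% for 0/12 and 4.3% to 48.1% for 3/15. The interval for 0/12 means nothing for this period, because the zero is not an observation. In a dose group of 4 with one early stopper, 0/4 becomes 1/5 (20%).

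**4. Other rows (any event, serious, device-related and so on).** If x of 12 continuing subjects and y of k early stoppers have the event, x/12 becomes (x + y)/(12 + k). This rises only when y/k exceeds x/12. Two assumed cases with k = 3:

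- x = 3, y = 3: 3/12 (25%) becomes 6/15 (40%).
- x = 9, y = 1: 9/12 (75%) becomes 10/15 (66.7%).

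The direction for these rows is therefore not fixed.

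**The case against.** The strongest reply is that the population fits the objective. Section 3.1 aims at subjects treated in HGT-SAN-055 who elect to continue, and following those children from first implantation describes their whole course. Early stoppers belong to HGT-SAN-055, whose own primary objective was safety and tolerability. The analysis is descriptive, with at most 12 subjects, and the programme has been stopped. Enlarging the safety population throughout would mix a few months of follow-up with years in one denominator.

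Much of this stands. The continuing-subject population is right for events during HGT-SAN-067 and for change from baseline, and it should be kept for both. What does not stand is carrying that population back, unlabelled, through the period that selected it. The SAP neither refers the reader to HGT-SAN-055 for the early stoppers nor calls its percentages conditional.

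A reader might also infer more than the documents support:

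- **That the tables present themselves as safety for everyone treated in the two studies.** No title in Appendix II says so. The combination comes from Sections 4.1 and 7.9.1.
- **That all early rates are biased downward.** This follows only for deaths and withdrawals in HGT-SAN-055. Step 4 shows that other rows can move either way.
- **That harm goes unreported.** The reporting of HGT-SAN-055 is not at hand. One can say only that this plan does not show it.
- **That defining membership by agreement rather than by a dose distorts the pooled tables.** It does not, because every member had already been treated in HGT-SAN-055. It matters only for a denominator confined to the extension.

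**Conclusion.** The point holds as a mismatch between the population and the event window. For the HGT-SAN-055 period, deaths and adverse-event withdrawals are zero by design, and the remaining adverse event percentages are conditional on completing and continuing, with bias of unknown direction.

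The size cannot be read from the SAP. The range of 0 to 3 excluded out of up to 15, or 0% to 20% for the discontinuation row, rests on planning figures and on all completers continuing. Completers who declined would add to the number excluded. A reader might take the 20% as what happened, but nothing in the SAP says that anyone stopped for harm. If nobody did, the death and discontinuation rows are unaffected.

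This is a moderate point. No hypothesis test or efficacy result depends on it, but it limits what the primary safety output can say about the first months after implantation.

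**What to change.** Keep the continuing-subject population for the extension objective and for change from baseline. Then amend Sections 6.2 and 7.9.1 and Appendices II and IV as follows:

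1. Split the summaries of treatment-emergent events, serious events, deaths and events leading to discontinuation by onset period.
2. For onset before the first HGT-SAN-067 dose, use as denominator all subjects implanted or dosed in HGT-SAN-055, whether or not they continued.
3. For onset on or after that dose, use subjects dosed in HGT-SAN-067.
4. Allocate events by onset date, not by the study whose record is used, because Section 4.1 replaces the HGT-SAN-055 record of an ongoing event with the HGT-SAN-067 record.
5. Label any whole-course percentage in continuing subjects as conditional on completing HGT-SAN-055 and continuing.
6. Report, by dose group, how many HGT-SAN-055 subjects did not continue and why.

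The cost is some SAP wording and one or two extra tables. HGT-SAN-055 data are already being pooled, though the records of subjects who did not continue would have to be included. The drawback is that early stoppers contribute shorter follow-up. Confining them to the early-period table limits this, and a footnote should state it.

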6.3 Handling of Missing Data

If data at the baseline visit are not available, then the most recent available pre-treatment visit will be considered as baseline. Missing or partial AE dates will not be imputed. However, a conservative approach will be adopted in such cases so that the AE will be deemed to be treatment emergent if it cannot be definitively categorized to have occurred prior to surgery for IDDD implantation.

7 Data Displays

Tabular summaries will be presented by rhHNS dose group (10 mg, 45 mg, 90 mg). Data listings will be presented for every dataset described under this section. Data listings will be sorted by rhHNS dose group, rhHNS dose, site number, and subject number.

7.1 Subject Disposition

The number of subjects who signed the informed consent, are in the safety population, completed the study, withdrawn from the study, and transitioned from 10 to 45 mg will be reported. Reasons for withdrawal will be tabulated.

Subject disposition will be presented in a by-subject listing.

7.2 Protocol Deviations

An incident involving noncompliance with the protocol, but one which typically does not have significant effect on the subject's rights, safety, or welfare, or the integrity of the resultant data will be considered a protocol deviation.

Protocol violations will be defined as any major protocol deviation that affects study evaluations, such as a significant violation of admission (inclusion/exclusion) criteria. Subjects will be examined on a case-by-case basis prior to final database lock to determine whether conditions set forth in the study protocol have been violated. If applicable, the determination of protocol violations will be performed by the Shire Human Genetic Therapies, Inc. (Shire HGT) Medical Monitor in consultation with the Study Biostatistician.

The protocol deviations will be presented in a listing and all protocol violations will be indicated by a flag.

7.3 Demographics and Other Baseline Characteristics

Demographic and baseline characteristics, eg, age (years), gender (male, female), race (American Indian or Alaskan Native, Asian, Black or African American, Native Hawaiian or other Pacific Islander, White, Other), ethnicity (Hispanic or Latino, Not Hispanic or Latino), weight (kg), height (cm) and head circumference (cm) will be summarized. Age, in years, will be calculated by subtracting the date of birth from the date of informed consent plus 1 and dividing by 365.25 and then rounding down to two decimal places.

Demographic information will be presented in a by-subject listing.

7.4 Medical History

A listing of medical and surgical histories will be provided for each subject.

7.5 Treatment Compliance and Extent of Exposure

Drug administration information will be presented by summarizing the duration of study drug exposure (weeks), the actual average dose (mg) and the number of infusions received.

The duration of IT administration is calculated by subtracting the IT administration start time from the IT administration end time.

By-subject listings of lot numbers of rhHNS received will be presented. A listing for drug administration including duration of administration will be presented by subject.

7.6 Analysis of Clinical Endpoints

7.6.1 Bayley Scales of Infant Development III (BSID-III)

The Bayley Scales of Infant Development is a standard series of measurements used primarily to assess the motor (fine and gross), language (receptive and expressive), and cognitive development of infants and toddlers, ages 0-42 months. This measure consists of a series of developmental play tasks and takes between 45 - 60 minutes to administer. Raw scores of successfully completed items will be converted to developmental age equivalent scores as well as composite scores, by referring to appropriate conversion tables in the BSID-III manual (Bayley, 2006). The mean composite score is 100 and the standard deviation (SD) is 15. Developmental Quotients (DQ) will be computed as a ratio, expressed as a percentage using the age equivalent score divided by the age at testing (i.e., [age equivalent score/chronological age] x 100).

Note that the determination of whether a subject received BSID-III or KABC-II at a particular assessment time was made based on an algorithm that includes the subject's calendar age and corresponding VABS-II age equivalent score. When the Bayley is used, the age equivalent scores and DQ scores for each subtest i.e. Cognitive, Receptive Communication, Expressive Communication, Fine Motor, and Gross Motor will be summarized at each assessment time point. The corresponding change from baseline at visits will be summarized as well. BSID-III data will be presented in a by-subject listing.

7.6.2 Kaufman Assessment Battery for Children II (KABC-II)

The Kaufman Assessment Battery for Children is an individually administered measure of the processing and reasoning abilities of children and adolescents between the ages of three and eighteen years. A detailed description of the KABC-II is provided in the KABC-II manual (Kaufman, 2004).

The KABC-II is an alternative to BSID-III. The KABC-II DQ scores, which are based on the average non-verbal age equivalent scores (see appendix I for additional details) will be combined with the BSID-III cognitive DQ scores and summarized at each assessment time point. The change from baseline at visits will be summarized as well. Similarly, the corresponding age-equivalent scores will be tabulated. Most of the subjects will have either only BSID-III data or KABC-II data. If a subject has data obtained by each of these methods, then the method for which data is available at both baseline and post-baseline time points will be used when combining the DQ scores and age-equivalent scores. KABC-II data will be presented in by-subject listings (3-6 years and 7-18 years).

Plots of mean BSID-III/KABC-II DQ scores across time will be presented. A spaghetti plot of DQ scores (and corresponding age-equivalent scores) of BSID-III/KABS-II against chronological age will be presented. On the graph the time when 10 mg subject switched to 45 mg will be indicated.

